8.3 Per Protocol Set

The Per Protocol Set (PP) is the subset of the FAS who fulfill key compliance criteria of the protocol and have no major protocol deviation that influences the evaluability of the study data. The major protocol deviations are described in “12.1 Major Protocol Deviations”. The Per Protocol will be analyzed by randomized study product.

8.4 Safety Set

The Safety Set consists of all patients enrolled with signed ICF who have at least one valid safety assessment during the course of the study. The Safety Set will be analyzed by actual exposure (see “product use pattern”).

Confidentiality Statement

Data and information contained in this document are considered to constitute trade secrets and confidential commercial information, and the legal protections provided to such trade secrets and confidential information are hereby claimed under the provisions of applicable law. No part of this document may be publicly disclosed without the written consent of Philip Morris Products S.A.

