## 6.2 Administration of Investigational Product(s)

The study is designed as an *ad libitum* use study. The patients will be allowed to use their allocated products (cigarette or IQOS) according to their need. Patients should be advised that when smoking cigarette or using IQOS, they should temporarily stop using the products in the event of any signs suggesting nicotine overexposure, (*e.g.*, gastrointestinal disturbance [nausea, vomiting, diarrhea, stomach or abdominal pain], cold sweats, headache, dizziness, breathing problems) or any reasons at the discretion of the Investigator.

Any patient who wish to stop smoking during the study will be encouraged to do so and referred to their General Practitioner for a smoking cessation program. This will not lead to discontinuation.

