### 8.2.2 Period of Collection

Any AEs (including SAEs) will be captured by the study site collaborators and assessed by the Investigator(s) or designee(s) in order to establish relationship to Investigational Products and study procedures. AEs will be collected from the time the patients have signed their ICFs until the end of the safety follow-up period.

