## **12.8 Safety Analysis**

In general, safety data will be provided in listings by exposure group, site, and patient. The data will be tabulated on the Safety Set by exposure group, using the approach described in section 12.1.3.

Adverse events data will serve as the primary assessment of safety.

The number and percentage of patients with AEs and SAEs will be tabulated by using the MedDRA® system organ class (SOC) and preferred term (PT), summarized for the Safety Set. Summaries will also be presented for AEs leading to discontinuation, AEs leading to death, AEs by relatedness to product exposure, and AEs by severity. Tabulations will be performed

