5.2.3 Monthly product consumption

Number of monthly product (HeatSticks, cigarette, other heat not burn products, e-cigarettes, smokeless tobacco pipe, smokeless tobacco, cigars/pipes/kiseru/shisha and nicotine replacement therapy) usage will be defined the daily average (see 5.2.2) multiplied by 30.

$$\left[\text{Monthly product consumption} = 30 * \frac{\text{Total product consumption}}{\text{Total number of days}} \right]$$

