9.1.3 Descriptive Statistics

9.1.3.1 Descriptive Statistics in general

For continuous data, summary statistics will include the number of patients [n], number and percentage of patients with missing data, the mean and standard deviation (SD), median, first and third quartiles, minimum and maximum, and 95% confidence interval (CI). The change from baseline will be presented as well. For confidence intervals calculated for bounded endpoints, for example, percentages which should be only between 0 and 100%, the CI's will be truncated to 0 if it is negative and 100% if it is greater than 100%.

Log-normally distributed data (*e.g.*, BoExp data) will also include the geometric mean, 95% CI of geometric mean, and coefficient of variation (CV) will be presented in addition to the mean and SD. The geometric relative change from baseline will be presented.

For categorical data, frequency counts and percentages will be presented.

Descriptive statistics will be presented by product exposure for As Exposed and Safety sets, by randomization arm for all other sets, and overall (across the entire study population) at each time point, where applicable.

Confidentiality Statement

Data and information contained in this document are considered to constitute trade secrets and confidential commercial information, and the legal protections provided to such trade secrets and confidential information are hereby claimed under the provisions of applicable law. No part of this document may be publicly disclosed without the written consent of Philip Morris Products S.A

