9.1.4 Definitions for Statistical Data Analysis

For periodontal parameters:

Six sites per tooth are to be evaluated. At least 4 of the 6 sites per tooth must be evaluated and have the measurements recorded for the tooth to be included in the assessment. If the site is evaluated and there is no PD to measure, the site must be recorded as 0 to indicate that there was no PD at the site (and to distinguish it from a site that was not evaluated).

When less than 4 sites are recorded, the assessment of the tooth will be considered as missing, and all periodontal assessments for that tooth will be excluded from the calculation of the means over all teeth (see Section 5.1.1).

For BoExp parameters:

Values below the lower limit of quantification (LLOQ) will be imputed using LLOQ/2. For

Confidentiality Statement

Data and information contained in this document are considered to constitute trade secrets and confidential commercial information, and the legal protections provided to such trade secrets and confidential information are hereby claimed under the provisions of applicable law. No part of this document may be publicly disclosed without the written consent of Philip Morris Products S.A.

values above the upper limit of quantification (ULOQ), the ULOQ will be imputed.

The number of values below LLOQ or above ULOQ will be presented in each summary table. If more than 50% of the data are below LLOQ, only the number and percentage of values below LLOQ will be reported in the summary together with the minimum and maximum values.

For calculation of creatinine adjusted BoExp if the denominator is below LLOQ then the ratio will not be calculated and will be tabulated as “Not Calculated” in descriptive summaries and excluded from the main analysis.

For self-reported tobacco or nicotine containing tobacco product use over the duration of the study data:

Only available data will be included in the product use summaries. Overall product exposure groups will be defined based on the data collected from randomization until EOS.

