9.5.4 Safety Evaluation

9.5.4.1 Safety Reporting

9.5.4.2 Adverse Events

For AE tables, tabulations will be performed for both the number and percentage of patients experiencing an event and the number of events experienced during the study period by Medical Dictionary for Regulatory Activities (MedDRA, Version 20.0 or higher) System Organ Class (SOC) - sorted by alphabetical order, Preferred Terms (PT) - sorted by alphabetical order. If there is a change in severity for an AE for a subject, that event is counted once at the worst severity. If a subject has AEs that occurs and resolves on multiple occasions, each AE is counted once at the highest severity. Unless otherwise noted, target population will be used as denominator for frequency table.

Confidentiality Statement

Data and information contained in this document are considered to constitute trade secrets and confidential commercial information, and the legal protections provided to such trade secrets and confidential information are hereby claimed under the provisions of applicable law. No part of this document may be publicly disclosed without the written consent of Philip Morris Products S.A

All AEs will be summarized by product use group, SOC and PT. The adverse events that occurred during the study will be broken down and reported in the following ways,

- Occurrence of serious adverse events
- Severity of adverse events
- Relatedness of adverse event to study procedure and investigational product
- Adverse events leading to discontinuation

The tables below show the various ways in which adverse events will be reported for the study.

Summary Table of Adverse Events		
Population	:	
 • Safety Sets 
 ➤ Product use pattern
Contents	:	
The number and percentage of patients experiencing an adverse event and the number of adverse events during the study period.
 
The overview table 15.2.10.1 includes a summary of overall number of AEs, SAEs, severity and relation to study procedure or investigational product and response to adverse events.
 
The summary table 15.2.10.2 shows a tabulation of adverse events by SOC/PT.

Output		
15.2.10.1 Overview Table of Adverse Events - Safety Set -
 
15.2.10.2 Summary Table of Adverse Events - Safety Set -
 
15.3.10.1 Listing of Adverse Events - Safety Set -

Summary Table of Adverse Events by Severity		

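### Adverse events are tabulated only by whole-study product use, a label set partly by what happens after the event; by-arm tables from Visit 2 should be added

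*SAP*

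**What the plan says.** **Grouping.** SAP 8.4 says of the safety population: "The Safety Set will be analyzed by actual exposure". SAP 9.5.4.2 applies this to AEs: "All AEs will be summarized by product use group, SOC and PT". Protocol 12.8 agrees: "The data will be tabulated on the Safety Set by exposure group". The general rule in SAP 9.1.3.1 keeps randomised arm for other populations: "Descriptive statistics will be presented by product exposure for As Exposed and Safety sets, by randomization arm for all other sets". Each AE display in SAP 9.5.4.2 to 9.5.4.2.2 (tables 15.2.10.1 to 15.2.10.9) names the product use pattern as its grouping. The table list in SAP 13.1.1 has no AE table by randomised arm and none by product in use at onset. The only Safety Set output titled by arm is demographics (15.2.2.4).

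**The label.** SAP 5.2 has four categories: cigarette, IQOS, dual and other. Monthly "usage will be defined the daily average (see 5.2.2) multiplied by 30" (SAP 5.2.3), where the daily average is total consumption after randomisation divided by days up to the last report (SAP 5.2.2). SAP 9.1.4 confirms the period: "Overall product exposure groups will be defined based on the data collected from randomization until EOS".

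**Collection.** Protocol 8.2.2: "AEs will be collected from the time the patients have signed their ICFs until the end of the safety follow-up period". Under Protocol 6.2.1 patients smoke their usual cigarettes until V2. In Table 4 of the Protocol they start the allocated product at the end of V2.

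**The concern.** A column headed IQOS user should show what happened to patients while they used IQOS. Here the column is filled by a whole-study average that includes use after the event. If an AE leads a patient to change product, the AE helps to decide which column it is reported in. The table of product-related AEs (15.2.10.3) uses the same label, so an event that the investigator judged related to IQOS can appear under another product.

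Two smaller gaps add to this. AEs between consent and V2 arise on cigarettes but are filed under whatever is used later. Patients enrolled but not randomised can belong to the Safety Set, yet they have no post-randomisation use from which to derive a category.

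Safety is a stated objective, and Protocol 12.8 makes AEs its primary assessment. For pocket depth, SAP 9.5.1.2 plans supportive analyses by randomised arm (Full Analysis Set and Per Protocol Set). For AEs nothing comparable is planned.

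**Working it through.** The plan states no figure to reproduce. The check has three parts.

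**1. Which label does a patient who switches receive?**
Inputs: the SAP 5.2.3 formula and 180 days of exposure (6 months of 30 days, Protocol 4.3). Assumed: c products per day throughout, HeatSticks for the first d days and then cigarettes.

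HeatSticks per month = 30 × c × d / 180 = c × d / 6. HeatStick share of use = d / 180.

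| Days on IQOS before return | c = 10 | c = 15 | c = 20 | Share |
|---|---|---|---|---|
| 7 | 11.7 | 17.5 | 23.3 | 3.9% |
| 30 | 50 | 75 | 100 | 16.7% |
| 90 | 150 | 225 | 300 | 50.0% |

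The cut-offs are in SAP Figure 2, which is not shown in the text available, so a HeatStick cut-off T between cigarette and dual user has to be assumed. The days on IQOS needed to reach it are d = 6T / c. For c = 10, 15 and 20:
- T = 10 per month: 6, 4, 3 days
- T = 30 per month: 18, 12, 9 days
- T = 60 per month: 36, 24, 18 days
- T = 100 per month: 60, 40, 30 days

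An early return to cigarettes can thus give cigarette user, and a later one dual user. By the same arithmetic, a return in the last days of the study may leave the label at IQOS user. So may withdrawal after the event with no cigarettes reported.

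**2. What can this do to the table?**
Assumed inputs: 86 per arm (the planned number), a first AE in 12 IQOS-arm and 6 cigarette-arm patients, six of the 12 change product afterwards, and nobody else switches.

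- By arm: 12/86 = 14.0% vs 6/86 = 7.0%.
- All six labelled dual: IQOS (12 − 6)/(86 − 6) = 6/80 = 7.5%; cigarette 6/86 = 7.0%; dual 6/6.
- All six labelled cigarette: IQOS 6/80 = 7.5%; cigarette (6 + 6)/(86 + 6) = 12/92 = 13.0%.
- One labelled cigarette and five dual: IQOS 6/80 = 7.5%; cigarette 7/87 = 8.0%.

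If fewer patients switch and all are labelled cigarette:
- Three: 9/83 = 10.8% vs 9/89 = 10.1%.
- Four: 8/82 = 9.8% vs 10/90 = 11.1%.

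For scale, the 10% non-adherence assumed in SAP 6 is about 9 of 86 per arm, from all causes.

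**3. How much falls before V2?**
V1 is 7 to 14 days before V2. At a constant event rate, the share of V1-to-V4 events that precede V2 is 7/(7 + 180) = 3.7% to 14/(14 + 180) = 7.2%. In an IQOS-user column these are cigarette-period events, so they raise the IQOS figure. Part 2 can lower it.

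**The case against.** Exposure grouping is prespecified and consistent between protocol and SAP. Safety is monitored descriptively, with no test whose result could change. Start dates, investigator causality and an AE listing (15.3.10.1) are kept, and an overall column is foreseen where applicable. If switchers become dual users, the dual column shows their events openly. Tables by arm have the converse fault: events in an IQOS-arm patient who has gone back to smoking count against IQOS.

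Most of this stands. It supports keeping the product-use tables and not insisting on arm as the main display. It does not remove the dependence of the label on later use, and a listing does not replace a comparison protected by randomisation.

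A reader might infer that these tables understate harm from IQOS by design, or count IQOS events against cigarettes. The documents do not support that:
- The dual category exists, and the cut-offs cannot be seen.
- The instruction sometimes read as driving a return to smoking is that "they should temporarily stop using the products in the event of any signs suggesting nicotine overexposure" (Protocol 6.2). It is temporary and covers both products. It shows that AEs may alter use, not that patients are sent back to cigarettes.
- Pre-V2 events push the IQOS column the other way.

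A reversed ranking of the two products might also be inferred from the example. It rests on assumed counts and labels: if all switchers are labelled cigarette users it takes at least four of the 12, and if all six are labelled dual it does not occur.

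**Conclusion.** The point holds as a limited one. All AE tables rest on a label that is partly fixed after the event. AEs before V2 are not separated, and never-randomised patients have no category. An AE on IQOS followed by a change of product can leave the IQOS-user column. In the assumed example an excess of 14.0% vs 7.0% by arm shrinks to 7.5% vs 7.0% when the six switchers are labelled dual, or becomes 7.5% vs 13.0% when they are labelled cigarette users. These figures illustrate what is possible. They do not predict the result, because the documents do not say how many AEs will lead to switching or where the Figure 2 cut-offs lie. The net direction and size are therefore unknown. This is a cheap improvement, not a fault that invalidates the safety reporting.

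**What to change.** Amend SAP 8.4, 9.5.4.2 and 13.1.1 as follows, and record the change in SAP 7.

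- Keep tables 15.2.10.1 to 15.2.10.9 by product use as prespecified.
- Add versions by randomised arm, for all randomised patients, of the overview and SOC/PT tables (15.2.10.1, 15.2.10.2), product-related AEs (15.2.10.3), serious AEs (15.2.10.5) and AEs leading to discontinuation (15.2.10.7). Count AEs with onset from first use of the allocated product at V2.
- Show AEs with onset before V2, and patients enrolled but never randomised, separately.
- Attribution to the product in use at onset is optional. Diaries are monthly totals on a 30-day or calendar month, with 2 days' flexibility (Protocol 7.5.7), so they cannot order events and switching within a month.

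The cost is more tables and a simple onset-date flag. SAP 9.1.5.2 does not impute partial AE dates, so the flag needs a stated rule for those. Arm, AE dates and diaries are already collected.

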8.5 Protocol Deviations

All protocol deviations will be entered into the Electronic Data Capture (EDC), Rave, by the CRAs.

Information from the source documents will represent the primary source of protocol deviations. Information following manual reviews after the event will be documented in follow-up letters, audit documentation and will be recorded and tracked in Rave. Telecommunications and other verbal communications regarding deviations will be considered and handled as important communication, and documented and tracked as protocol deviations, as necessary.

Individual entries for protocol deviations that are recorded in Rave, following site monitoring and other manual reviews will be reviewed against the individual data points in the Case Report Form (CRF) database by PMI but will not be formally reconciled with the CRF database (*e.g.*, their description or occurrence date).

The overall procedures for managing protocol deviations are described in the SOPs, Data Management Plan (DMP) and Clinical Monitoring Plan of the CRO. All deviations will be reviewed periodically by PMI, as determined at study start, to identify trends to improve monitoring and/or potential impact on the statistical analysis.

8.5.1 Major Protocol Deviations

Major protocol deviations are protocol deviations that may significantly impact the completeness, accuracy, and/or reliability of the study data or that may significantly affect a patient's rights, safety, or well-being.

Patients with major PDs below will be identified to determine whether they will be excluded from any of the analysis sets.

The following general rules will be applied to determine if a deviation was major:

Confidentiality Statement

Data and information contained in this document are considered to constitute trade secrets and confidential commercial information, and the legal protections provided to such trade secrets and confidential information are hereby claimed under the provisions of applicable law. No part of this document may be publicly disclosed without the written consent of Philip Morris Products S.A

1. If more than 2 out of 6 sites at a measured tooth were not evaluated, then it will be considered major, evaluable.
2. Protocol violations pertaining to inclusion/exclusion criteria will considered major deviations, evaluable if no results or safety is impacted.
3. Protocol violations pertaining to ICF will be considered major deviations, evaluable if no results or safety is impacted. If the ICF was not signed then the patient will be major, non-evaluable.
4. Samples that were destroyed in error were considered major, evaluable.

8.5.2 Minor Protocol Deviations

Minor protocol deviations are defined as deviation that does not impact any of the following: (1) the safety of a patient participating the study; (2) the integrity of the data collected for the evaluation of the study; or (3) the overall evaluation and/or interpretation of the outcome of the study, specifically with respect to the primary objective.

Confidentiality Statement

Data and information contained in this document are considered to constitute trade secrets and confidential commercial information, and the legal protections provided to such trade secrets and confidential information are hereby claimed under the provisions of applicable law. No part of this document may be publicly disclosed without the written consent of Philip Morris Products S.A

9 PLANNED STATISTICAL METHODS

9.1 General Considerations

Data analysis will be performed using SAS® Version 9.2 or higher.

9.1.1 Stratified Presentation

For the primary analysis of PD, the following stratification criteria will be used:

1. Daily cigarette consumption over the month (30 days) prior to V1 (10-19 cigarettes/day vs. >19 cigarettes/day)
2. Disease severity in smokers with generalized chronic periodontitis (< 5 mm vs. ≥ 5 mm PD).

9.1.2 Sub-group Analyses

The following factors will be used for the sub group analysis.

- Sex (Male/Female)
- Age ($30 \leq <40$, $40 \leq <50$, $50 \leq <60$, $60 \geq$)

9.1.3 Descriptive Statistics

9.1.3.1 Descriptive Statistics in general

For continuous data, summary statistics will include the number of patients [n], number and percentage of patients with missing data, the mean and standard deviation (SD), median, first and third quartiles, minimum and maximum, and 95% confidence interval (CI). The change from baseline will be presented as well. For confidence intervals calculated for bounded endpoints, for example, percentages which should be only between 0 and 100%, the CI's will be truncated to 0 if it is negative and 100% if it is greater than 100%.

Log-normally distributed data (*e.g.*, BoExp data) will also include the geometric mean, 95% CI of geometric mean, and coefficient of variation (CV) will be presented in addition to the mean and SD. The geometric relative change from baseline will be presented.

For categorical data, frequency counts and percentages will be presented.

Descriptive statistics will be presented by product exposure for As Exposed and Safety sets, by randomization arm for all other sets, and overall (across the entire study population) at each time point, where applicable.

Confidentiality Statement

Data and information contained in this document are considered to constitute trade secrets and confidential commercial information, and the legal protections provided to such trade secrets and confidential information are hereby claimed under the provisions of applicable law. No part of this document may be publicly disclosed without the written consent of Philip Morris Products S.A

9.1.3.2 Descriptive Statistics for Exploratory Analysis

Descriptive statistics will be reported by product exposure and strata, and will include basic descriptive statistics such as the sample size, the sample mean, standard deviation, standard error of the mean, and CV. Robust measures for the center (median) and the dispersion (median absolute deviation, MAD) of the data will be also included.

9.1.3.3 Median Absolute Deviation (MAD)

Calculate median absolute deviation with the following equation.

$$[\text{MAD} = \text{median} (|X_i - \text{median}(X)|)]$$

where X_i is a sequence of observations ($i = 1, \dots, n$) for the variable X .

